## C. Determination of tumor response by FDG-PET/CT using PERCIST 1.0

Subjects in this research study will undergo  $^{18}\text{F}$ -FDG-PET/CT at baseline, cycle 3, and off-study as per the research protocol. Images will be analyzed by nuclear medicine radiologist and metabolic response determined by PERCIST 1.0 (Wahl et al, J Nucl Med 2009).

Selection of target and non-target lesions:

Measurable target lesion is the hottest single tumor lesion with maximal ROI of 1.2 cm in diameter (SUL peak). SUL peak should be at least 1.5 times higher than liver SUL mean + 2 SD. Up to five target lesions may be selected with no more than 2 per organ. These lesions will be compared in subsequent scans.

Response criteria:

Response category	Description
CMR	Complete resolution of FDG uptake within target lesion to indistinguishable levels compared to background blood-pool and liver. Disappearance of all metabolic lesions. No new lesions in the pattern of cancer.
PMR	Reduction of target lesion SUL peak by $\geq 30\%$
SMD	Not CMR, PMR, or PMD
PMD	>30% increase in target lesion SUL peak. OR increase in TLG volume with no change in SUL. OR appearance of new lesions.

[figure not shown]
**Table F5. PERCIST 1.0 for determination of metabolic response.** (Adapted from Wahl et al, J Nucl Med 2009).

**C. Exploratory Objective 3: Measurement of circulating tumor cells pre- and post-treatment, and correlation with tumor response and time to progression**

Rationale:

Circulating tumor cells (CTC) have been shown to be prognostic of metastatic disease and correlate with response to therapy in solid tumors such as breast, colorectal and prostate cancers. However, assessment of CTCs is challenging in sarcoma due to the lack of universal markers. In collaboration with [name], we have demonstrated in a pilot study (Eprost 20140062) that sarcoma circulating tumor cells are large and can be isolated using a unique, microfabricated parylene membrane-based device (Figure F2). The hypothesis for this pilot study is that CTC could serve as a marker of early micrometastatic disease in sarcomas, and may portend worse prognosis as seen in other tumor types.

**Figure F3. Circulating tumor cell identified from a patient with metastatic dedifferentiated chondrosarcoma.** (Courtesy of [name], unpublished data)

We will collect data for circulating tumor cells as part of this axitinib/pembrolizumab study, in hopes that a more effective CD8+ anti-tumor effect could decrease the presence of circulating tumor cells and decrease development of new metastatic sites. Thus, peripheral blood samples will be drawn at selected timepoints and filtered to detect the numbers of circulating tumor cells using this technology. The presence or absence of CTC will be correlated with tumor response.

Approach:

- a. Peripheral blood will be collected into CellSave tubes as detailed in the protocol and immediately transferred to [name] laboratory.
- b. Samples will be diluted 1:1 in PBS and briefly fixed in 1% formalin at room temperature for ten minutes.
- c. Following fixation, the blood samples will be passed through the microfilter device at constant low flow rate using a syringe pump.
- d. The microfilter will be disengaged from its housing cassette and placed onto a glass microscope slides for analysis.
- e. Samples will be stained for H&E analysis and reviewed with an expert sarcoma pathologist to identify and quantify circulating tumor cells. Where appropriate, additional immunocytochemistry will be performed using cell surface vimentin or other marker based on specific histology.

**D. Data and specimen banking for later correlative analyses**

- a. Any additional samples, such as an extra core biopsy, or any patients that have surgery at any time along the protocol will have tissue samples banked. If possible, tissue will be frozen viably, for RNA in RNA later, and flash frozen for protein analysis. Additionally blood samples will be banked in the [name] lab as part of the PBMC protocol as detailed above.
- b. Upon collection of all samples from the patients, a bar code system will be used to code the samples, assigning a subject number and bar code to each specimen. The actual physical samples will be tied to patient identifying information only at the time of sample collection. The patient's name will be written on the specimen collection tubes. Once the samples are coded, immediately following sample collection, the patient's name will be blacked out on the original sample tubes and the original tubes will be disposed of in the biohazardous waste, which gets sent for incineration.
- c. The database linking subject identification and specimen barcodes will be kept on a password protected database housed on the University of Miami server.
- d. The only investigators who will have access to samples and linking data to subjects are the principal investigator and his research staff named on the protocol. The tissue bank database will be the only location where patient's names and medical record numbers will be tied to their barcode numbers. The only information that will be stored with the actual samples in the freezers is the barcode identifier used to identify each sample. Data and specimens will be maintained indefinitely. If at some point in time, a subject decides they wish to remove their specimens and data from the tissue bank, any remaining samples belonging to that patient will be destroyed and their data removed from the database.

## **APPENDIX G: PROTOCOL APPROVED METHODS OF CONTRACEPTION**

### **Pembrolizumab**

Pembrolizumab may have adverse effects on a fetus in utero. Furthermore, it is not known if pembrolizumab has transient adverse effects on the composition of sperm. Non-pregnant, non-breast-feeding women may be enrolled if they are willing to use 2 methods of birth control or are considered highly unlikely to conceive. Highly unlikely to conceive is defined as 1) surgically sterilized, or 2) postmenopausal (a woman who is  $\geq 45$  years of age and has not had menses for greater than 1 year will be considered postmenopausal), or 3) not heterosexually active for the duration of the study. The two birth control methods can be either two barrier methods or a barrier method plus a hormonal method to prevent pregnancy. Subjects should start using birth control from study Visit 1 throughout the study period up to 120 days after the last dose of study therapy.

The following are considered adequate barrier methods of contraception: diaphragm, condom (by the partner), copper intrauterine device, sponge, or spermicide. Appropriate hormonal contraceptives will include any registered and marketed contraceptive agent that contains an estrogen and/or a progestational agent (including oral, subcutaneous, intrauterine, or intramuscular agents).

Subjects should be informed that taking the study medication may involve unknown risks to the fetus (unborn baby) if pregnancy were to occur during the study. In order to participate in the study they must adhere to the contraception requirement (described above) for the duration of the study and within 120 days of completing the trial, or 30 days following cessation of treatment if the subject initiates new anticancer therapy, whichever is earlier. If there is any question that a subject will not reliably comply with the requirements for contraception, that subject should not be entered into the study.

### **Use in Pregnancy**

If a subject inadvertently becomes pregnant while on treatment with pembrolizumab, the subject will immediately be removed from the study. The site will contact the subject at least monthly and document the subject's status until the pregnancy has been completed or terminated. The outcome of the pregnancy will be reported to the Sponsor and to Merck without delay and within 24 hours to the Sponsor and within 2 working days to Merck if the outcome is a serious adverse experience (e.g., death, abortion, congenital anomaly, or other disabling or life-threatening complication to the mother or newborn). The study investigator will make every effort to obtain permission to follow the outcome of the pregnancy and report the condition of the fetus or newborn to the Sponsor. If a male subject impregnates his female partner the study personnel at the site must be informed immediately and the pregnancy reported to the Sponsor and to Merck and followed as described above.

**Use in Nursing Women**

It is unknown whether pembrolizumab is excreted in human milk. Since many drugs are excreted in human milk, and because of the potential for serious adverse reactions in the nursing infant, subjects who are breast-feeding are not eligible for enrollment.

## **APPENDIX H: EVENTS OF CLINICAL INTEREST & SUPPORTIVE CARE GUIDELINES FOR PEMBROLIZUMAB**

Suggested supportive care measures for the management of AEs with potential immunologic etiology. Where appropriate, these guidelines include the use of oral or intravenous treatment with corticosteroids as well as additional anti-inflammatory agents if symptoms do not improve with administration of corticosteroids. These guidelines are intended to be applied when the Investigator determines the events to be related to pembrolizumab.

- **Pneumonitis:**
  - For **Grade 2 events**, treat with systemic corticosteroids. When symptoms improve to Grade 1 or less, steroid taper should be started and continued over no less than 4 weeks.
  - For **Grade 3-4 events**, immediately treat with intravenous steroids. Administer additional anti-inflammatory measures, as needed.
  - Add prophylactic antibiotics for opportunistic infections in the case of prolonged steroid administration.
  
- **Diarrhea/Colitis:**

Subjects should be carefully monitored for signs and symptoms of enterocolitis (such as diarrhea, abdominal pain, blood or mucus in stool, with or without fever) and of bowel perforation (such as peritoneal signs and ileus).

  - All subjects who experience diarrhea/colitis should be advised to drink liberal quantities of clear fluids. If sufficient oral fluid intake is not feasible, fluid and electrolytes should be substituted via IV infusion. For Grade 2 or higher diarrhea, consider GI consultation and endoscopy to confirm or rule out colitis.
  - For **Grade 2 diarrhea/colitis** that persists greater than 3 days, administer oral corticosteroids.
  - For **Grade 3 or 4 diarrhea/colitis** that persists > 1 week, treat with intravenous steroids followed by high dose oral steroids.
  - When symptoms improve to Grade 1 or less, steroid taper should be started and continued over no less than 4 weeks.
  
- **Type 1 diabetes mellitus (if new onset, including diabetic ketoacidosis [DKA]) or ≥ Grade 3 Hyperglycemia, if associated with ketosis (ketonuria) or metabolic acidosis (DKA)**
  - For **T1DM or Grade 3-4 Hyperglycemia**
    - Insulin replacement therapy is recommended for Type I diabetes mellitus and for Grade 3-4 hyperglycemia associated with metabolic acidosis or ketonuria.

- Evaluate patients with serum glucose and a metabolic panel, urine ketones, glycosylated hemoglobin, and C-peptide.
- **Hypophysitis:**
  - For **Grade 2** events, treat with corticosteroids. When symptoms improve to Grade 1 or less, steroid taper should be started and continued over no less than 4 weeks. Replacement of appropriate hormones may be required as the steroid dose is tapered.
  - For **Grade 3-4** events, treat with an initial dose of IV corticosteroids followed by oral corticosteroids. When symptoms improve to Grade 1 or less, steroid taper should be started and continued over no less than 4 weeks. Replacement of appropriate hormones may be required as the steroid dose is tapered.
- **Hyperthyroidism or Hypothyroidism:**

Thyroid disorders can occur at any time during treatment. Monitor patients for changes in thyroid function (at the start of treatment, periodically during treatment, and as indicated based on clinical evaluation) and for clinical signs and symptoms of thyroid disorders.

  - **Grade 2** hyperthyroidism events (and **Grade 2-4** hypothyroidism):
    - In hyperthyroidism, non-selective beta-blockers (e.g. propranolol) are suggested as initial therapy.
    - In hypothyroidism, thyroid hormone replacement therapy, with levothyroxine or liothyronine, is indicated per standard of care.
  - **Grade 3-4** hyperthyroidism
    - Treat with an initial dose of IV corticosteroid followed by oral corticosteroids. When symptoms improve to Grade 1 or less, steroid taper should be started and continued over no less than 4 weeks. Replacement of appropriate hormones may be required as the steroid dose is tapered.
- **Hepatic:**
  - For **Grade 2** events, monitor liver function tests more frequently until returned to baseline values (consider weekly).
    - Treat with IV or oral corticosteroids
  - For **Grade 3-4** events, treat with intravenous corticosteroids for 24 to 48 hours.
  - When symptoms improve to Grade 1 or less, a steroid taper should be started and continued over no less than 4 weeks.
  - An elevated AST or ALT lab value that is  $\geq 3X$  the upper limit of normal (ULN) **and** an elevated total bilirubin lab value that is  $\geq 2X$  the ULN and, at the same time, an alkaline phosphatase lab value that is  $< 2X$  the ULN, as determined by way of protocol-specified laboratory testing or unscheduled laboratory testing.\*

\*Note: These criteria are based upon available regulatory guidance documents. The purpose of the criteria is to specify a threshold of abnormal hepatic tests that may require an additional evaluation for an underlying etiology. The trial site guidance for assessment and follow up of these criteria can be found in the Investigator Trial File Binder (or equivalent).

- **Renal Failure or Nephritis:**
  - For **Grade 2** events, treat with corticosteroids.
  - For **Grade 3-4** events, treat with systemic corticosteroids.
  - When symptoms improve to Grade 1 or less, steroid taper should be started and continued over no less than 4 weeks.
- **Management of Infusion Reactions:** Signs and symptoms usually develop during or shortly after drug infusion and generally resolve completely within 24 hours of completion of infusion.

**Table H1** below shows treatment guidelines for subjects who experience an infusion reaction associated with administration of pembrolizumab (MK-3475).

NCI CTCAE Grade	Treatment	Premedication at subsequent dosing
Grade 1 Mild reaction; infusion interruption not indicated; intervention not indicated	Increase monitoring of vital signs as medically indicated until the subject is deemed medically stable in the opinion of the investigator.	None
Grade 2 Requires infusion interruption but responds promptly to symptomatic treatment (e.g., antihistamines, NSAIDS, narcotics, IV fluids); prophylactic medications indicated for <=24 hrs	Stop Infusion and monitor symptoms. Additional appropriate medical therapy may include but is not limited to: 
 
IV fluids
 
Antihistamines
 
NSAIDS
 
Acetaminophen
 
Narcotics
 
 Increase monitoring of vital signs as medically indicated until the subject is deemed medically stable in the opinion of the investigator.	Subject may be premedicated 1.5h (± 30 minutes) prior to infusion of pembrolizumab (MK-3475) with:  Diphenhydramine 50 mg po (or equivalent dose of antihistamine).  Acetaminophen 500-1000 mg po (or equivalent dose of antipyretic).

NCI CTCAE Grade	Treatment	Premedication at subsequent dosing
	
If symptoms resolve within one hour of stopping drug infusion, the infusion may be restarted at 50% of the original infusion rate (e.g., from 100 mL/hr to 50 mL/hr). Otherwise dosing will be held until symptoms resolve and the subject should be premedicated for the next scheduled dose.
 
Subjects who develop Grade 2 toxicity despite adequate premedication should be permanently discontinued from further trial treatment administration.
	

Grades 3 or 4
 
Grade 3: Prolonged (i.e., not rapidly responsive to symptomatic medication and/or brief interruption of infusion); recurrence of symptoms following initial improvement; hospitalization indicated for other clinical sequelae (e.g., renal impairment, pulmonary infiltrates)
 
Grade 4: Life-threatening; pressor or ventilatory support indicated
	
Stop Infusion. Additional appropriate medical therapy may include but is not limited to:
 
 
IV fluids
 
Antihistamines
 
NSAIDS
 
Acetaminophen
 
Narcotics
 
Oxygen
 
Pressors
 
Corticosteroids
 
Epinephrine
 
 
Increase monitoring of vital signs as medically indicated until the subject is deemed medically stable in the opinion of the investigator. Hospitalization may be indicated.
 
Subject is permanently discontinued from further trial treatment administration.
	
No subsequent dosing

NCI CTCAE Grade	Treatment	Premedication at subsequent dosing
Appropriate resuscitation equipment should be available in the room and a physician readily available during the period of drug administration.		

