### **Clinical Trials Experience**

The safety of KEYTRUDA was investigated in two controlled, randomized studies (KEYNOTE-002 and KEYNOTE-006) for the treatment of unresectable or metastatic melanoma and in an uncontrolled, open-label study (KEYNOTE-001) for the treatment of unresectable or metastatic melanoma and metastatic non-small cell lung carcinoma (NSCLC). Overall, 1567 subjects with melanoma (699 previously treated with ipilimumab and 868 naïve to ipilimumab) and 550 subjects with NSCLC were treated. Safety is described for the pooled population of 2117 subjects (studied across three doses; 2 mg/kg every 3 weeks and 10 mg/kg every 2 or 3 weeks). The median treatment duration was 4.6 months (range 1 day to 28.3 months) including 906 subjects treated for greater than or equal to 6 months and 203 subjects treated for greater than or equal to one year.

KEYTRUDA was discontinued for treatment-related adverse reactions in 4% of subjects. Treatment-related serious adverse events (SAEs) reported up to 90 days after the last dose occurred in 9% of subjects receiving KEYTRUDA. Of these treatment-related SAEs, those occurring in more than five subjects (out of 2117) were pneumonitis (n=24), colitis (n=19), diarrhea (n=16), pyrexia (n=8), adrenal insufficiency (n=6) and autoimmune hepatitis (n=6).

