### **Immune-Mediated Colitis**

Colitis (including microscopic colitis) occurred in 4 (1%) of 411 patients, including Grade 2 or 3 cases in 1 (0.2%) and 2 (0.5%) patients, respectively, receiving KEYTRUDA in Trial 1. The median time to onset of colitis was 6.5 months (range 2.3-9.8). The median duration was 2.6 months (range 0.6 weeks-3.6 months). All three patients with Grade 2 or 3 colitis were treated with high-dose corticosteroids (greater than or equal to 40 mg prednisone or equivalent per day) with a median initial dose of 70 mg/day of prednisone or equivalent; the median duration of initial treatment was 7 days (range 4-41), followed by a corticosteroid taper. One patient (0.2%) required permanent discontinuation of KEYTRUDA due to colitis. All four patients with colitis experienced complete resolution of the event. Monitor patients for signs and symptoms of colitis. Administer corticosteroids for Grade 2 or greater colitis. Withhold KEYTRUDA for moderate (Grade 2) or severe (Grade 3) colitis, and permanently discontinue KEYTRUDA for life-threatening (Grade 4) colitis.

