**Table 12. Dose Modification and Toxicity Management Guidelines for Immune-Related AEs Associated with Pembrolizumab.**

General instructions:				

 
1. Corticosteroid taper should be initiated upon AE improving to Grade 1 or less and continue to taper over at least 4 weeks.
 
2. For situations where pembrolizumab has been withheld, pembrolizumab can be resumed after AE has been reduced to Grade 1 or 0 and corticosteroid has been tapered. Pembrolizumab should be permanently discontinued if AE does not resolve within 12 weeks of last dose or corticosteroids cannot be reduced to <math>\leq 10</math> mg prednisone or equivalent per day within 12 weeks.
 
3. For severe and life-threatening irAEs, IV corticosteroid should be initiated first followed by oral steroid. Other immunosuppressive treatment should be initiated if irAEs cannot be controlled by corticosteroids.
 
				
Immune-related AEs	Toxicity grade or conditions (CTCAEv4.0)	Action taken to pembrolizumab	irAE management with corticosteroid and/or other therapies	Monitor and follow-up
Steven-Johnson Syndrome (SJS)	Any	Permanently discontinue	Refer patient for specialized care for assessment and treatment.	If SJS confirmed, permanently discontinue pembrolizumab
Toxic Epidermal Necrolysis (TEN)	Any	Permanently discontinue	Refer patient for specialized care for assessment and treatment.	If TEN confirmed, permanently discontinue pembrolizumab
Pneumonitis	Grade 2	Withhold	Administer corticosteroids (initial dose of 1-2 mg/kg prednisone or equivalent) followed by taper	
Monitor participants for signs and symptoms of pneumonitis
 
Evaluate participants with suspected pneumonitis with radiographic imaging and initiate corticosteroid treatment
 
Add prophylactic antibiotics for opportunistic infections

	Grade 3 or 4, or recurrent Grade 2	Permanently discontinue		

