Diarrhea / Colitis	Grade 2 or 3	Withhold	Administer corticosteroids (initial dose of 1-2 mg/kg prednisone or equivalent) followed by taper	
 
• Monitor participants for signs and symptoms of enterocolitis (ie, diarrhea, abdominal pain, blood or mucus in stool with or without fever) and of bowel perforation (ie, peritoneal signs and ileus).
 
• Participants with <math>\geq</math> Grade 2 diarrhea suspecting colitis should consider GI consultation and performing endoscopy to rule out colitis.
 
• Participants with diarrhea/colitis should be advised to drink liberal quantities of clear fluids. If sufficient oral fluid intake is not feasible, fluid and electrolytes should be substituted via IV
 

	Grade 4	Permanently discontinue		infusion.
AST / ALT elevation	3	Withhold	Administer corticosteroids (initial dose of 0.5- 1 mg/kg prednisone or equivalent) followed by taper	Monitor with liver function tests (consider weekly or more frequently until liver enzyme value returned to baseline or is stable
	4	Permanently discontinue --see exception below 	Administer corticosteroids (initial dose of 1-2 mg/kg prednisone or equivalent) followed by taper	
Increased bilirubin	Grade 2	Withhold	Administer corticosteroids (initial dose of 0.5- 1 mg/kg prednisone or equivalent) followed by taper	Monitor with liver function tests (consider weekly or more frequently until liver enzyme value returned to baseline or is stable
	Grade 3 or 4	Permanently discontinue	Administer corticosteroids (initial dose of 1-2 mg/kg prednisone or equivalent) followed by taper	
Type 1 diabetes mellitus (T1DM) or Hyperglycemia	Newly onset T1DM or Grade 3 or 4 hyperglycemia associated with evidence of $\beta$ -cell failure	Withhold	Initiate insulin replacement therapy for participants with T1DM  Administer anti-hyperglycemic in participants with hyperglycemia	Monitor participants for hyperglycemia or other signs and symptoms of diabetes.
Hypophysitis	Grade 2	Withhold	Administer corticosteroids and initiate hormonal replacements as clinically indicated.	Monitor for signs and symptoms of hypophysitis (including hypopituitarism and adrenal insufficiency)
	Grade 3 or 4	Withhold or permanently discontinue 		

Hyperthyroidism	Grade 2	Continue	Treat with non-selective beta-blockers (eg, propranolol) or thionamides as appropriate	Monitor for signs and symptoms of thyroid disorders.

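### Appendix H starts steroids for grade 3-4 diarrhea/colitis only after more than a week, longer than at grade 2; Table 12 sets no wait, and Section 10.3 does not say which governs

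*Combined protocol and SAP*

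**What the plan says.** Appendix H opens by limiting its scope: "These guidelines are intended to be applied when the Investigator determines the events to be related to pembrolizumab". Under Diarrhea/Colitis it gives two steroid triggers. At grade 3-4 the wording is "that persists > 1 week, treat with intravenous steroids followed by high dose oral steroids". At grade 2, which comes earlier in the list, it is "that persists greater than 3 days, administer oral corticosteroids".

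Three other places address the same event:

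- Table 12, diarrhea/colitis row: "Administer corticosteroids (initial dose of 1-2 mg/kg prednisone or equivalent) followed by taper", with pembrolizumab withheld at grade 2 or 3 and permanently stopped at grade 4.
- Table 12, general instruction 3: "For severe and life-threatening irAEs, IV corticosteroid should be initiated first followed by oral steroid".
- Section 9.2.4, Immune-Mediated Colitis: "Administer corticosteroids for Grade 2 or greater colitis".

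Section 10.3 sends the reader to its dose-modification table and adds a see-also reference to Appendix H. It does not say which prevails if they differ. Both Section 8.6 and Appendix H describe the supportive-care measures as suggested.

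**The concern.** A longer wait at a higher grade is the reverse of what one expects in managing an immune-related event. Section 9.2.4 itself says that recognizing these events and starting treatment early is critical to limiting complications. An investigator who follows the Appendix H line literally could hold steroids for more than seven days in a severe immune-related colitis. One who follows Table 12 would meet no such condition. Both texts sit in the same protocol, so two patients with the same event could be managed differently, each in line with it. What is at stake is patient safety, not the analysis.

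**Working it through.** The plan gives no figure to reproduce. The check is a comparison of texts, followed by a rough count of how often the line could apply.

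**Step 1. The texts side by side.**

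| Source | Grade | Condition on duration before steroids |
|---|---|---|
| Appendix H, diarrhea/colitis | 2 | more than 3 days |
| Appendix H, diarrhea/colitis | 3-4 | more than 1 week (7 days) |
| Table 12, diarrhea/colitis | 2-3 | none stated |
| Table 12, general instruction 3 | severe and life-threatening | none stated |
| Section 9.2.4, colitis | 2 or greater | none stated |

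The grade 3-4 threshold exceeds the grade 2 threshold by 7 − 3 = 4 days. The three sources without a condition are silent on timing; they do not say that steroids must start at once. In the text available, Table 12's steroid entry stands beside grade 2 or 3 and the grade 4 cell is empty, which may be a merged cell. General instruction 3 covers grade 4 either way.

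**Step 2. The rest of Appendix H.** For grade 3-4 pneumonitis, intravenous steroids are immediate. The grade 3-4 lines for hypophysitis, hyperthyroidism, hepatic events and nephritis state no wait. Diarrhea/colitis is the only exception.

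**Step 3. Which text is newer.** Appendix H cites a pembrolizumab guidance document dated December 2014. The revision history says that the dose-modification table was updated in the March 2018 version after a November 2017 letter, and it names no Appendix H change. This suggests that the appendix line was left behind, but does not prove it.

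**Step 4. How many patients could meet the line.** The documents give no rate for the combination, so I assume that the single-agent pembrolizumab rates in Section 9.2.4 apply. The colitis text reports 411 patients, "including Grade 2 or 3 cases in 1 (0.2%) and 2 (0.5%) patients, respectively". The pooled safety text reports 19 treatment-related serious colitis and 16 serious diarrhea events among 2117 subjects. With rate p and n patients, the expected number is n × p and the chance of at least one is 1 − (1 − p)^n.

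| Rate used | p | Expected, n = 10 | At least one, n = 10 | Expected, n = 40 | At least one, n = 40 |
|---|---|---|---|---|---|
| Grade 3 colitis, 2/411 | 0.00487 | 0.05 | 5% | 0.19 | 18% |
| Serious colitis, 19/2117 | 0.00897 | 0.09 | 9% | 0.36 | 30% |
| Serious colitis plus diarrhea, no overlap, 35/2117 | 0.01653 | 0.17 | 15% | 0.66 | 49% |

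The values 10 (the expansion) and 40 (all evaluable patients) are illustrative. Section 1.5 says that 30 patients had accrued before the expansion, and the documents do not say how many remain on pembrolizumab. Serious is also not the same as grade 3-4.

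**The case against.** The best defence is that axitinib also causes diarrhea, so a period of watching is sensible. Section 10.1 names diarrhea/colitis among the toxicities possibly due to both drugs and has axitinib interrupted first. Section 10.2 allows 3 days of supportive care before an axitinib reduction and a 3-5 day hold, particularly at grade 3. Added together, these give 3 + 3 = 6 to 3 + 5 = 8 days, which is about a week. Table 5 uses 7 days as well: grade 3 or higher diarrhea controlled by medication within that time is not a DLT. Section 8.6 counts a possible relation as related, so Appendix H can apply while axitinib is still suspected.

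This carries weight. It supports a short trial of supportive care and an axitinib hold, and it makes the grade 2 three-day trigger defensible. It would be wrong to say that the axitinib steps cannot account for any delay at grade 3, or that every event under Appendix H has been settled as pembrolizumab's alone. But Section 10.2 governs axitinib dosing and sets no steroid wait, and Table 5 defines DLTs. Section 10.1 says that axitinib toxicity generally resolves promptly on interruption and, if it persists, routes the reader to the pembrolizumab guidelines, where the two texts differ. None of this reaches grade 4, where Table 11 stops axitinib.

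A second defence is that a suggested appendix, reached by a see-also reference, yields to three instructions elsewhere, and that sites receive a separately updated guidance document. Many readers would resolve it that way, and that document was not available for this review. The protocol still does not say so.

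**Conclusion.** The inconsistency is real and worth fixing. At grade 3-4, Appendix H sets a wait of more than 7 days that Table 12, general instruction 3 and Section 9.2.4 do not share, and no sentence ranks them. The textual mismatch is certain. The clinical consequence is less so, because it depends on which text an investigator follows and on a guidance document not seen here.

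Three stronger readings are tempting but not supported:

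- A reader might infer that severe colitis goes unmanaged for a week. It does not: pembrolizumab is withheld or stopped, Appendix H calls for fluids, watching for perforation and considering gastroenterology consultation, and nothing forbids earlier steroids.
- A reader might take the 5% to 49% range as the chance of harm. Those are chances of any qualifying event under borrowed single-agent rates, not of a steroid delay caused by this line.
- A reader might expect an effect on the results. No estimate, power or error rate changes.

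**What to change.** With medical team confirmation:

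1. In the Appendix H grade 3-4 diarrhea/colitis line, delete the condition that the event has lasted more than a week.
2. In Section 10.3, state that for grade 3-4 diarrhea/colitis Table 12 and general instruction 3 govern, subject to the axitinib interruption step in Section 10.1 when both drugs may be the cause.
3. Leave the grade 2 three-day trigger as it is unless the medical team revises it. The precedence sentence is limited to grade 3-4 because a blanket one would override that trigger.

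The same amendment can tidy two pointers in Section 10.3: Table 10 is now the axitinib titration table and should read Table 12, and Section 8.4 should read Section 8.6. These are clerical. The cost is amendment wording only, with no new data, visits or patients.
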